5.13. Pregnancy

Fertility and reproduction studies in animals have revealed no evidence of impaired fertility or harm to the fetus due to NTZ. However, there are no adequate and well controlled studies of fertility or reproduction in humans. All pregnancies including those of partners of male subjects included in the study will be reported by the investigational staff within 24 hours of their knowledge of the event using a pregnancy reporting form.

6. RANDOMIZATION

An independent third party (██████████) will prepare a master randomization list and maintain the masking of the study. Randomization will be performed using permuted block randomization. Subjects who qualify for the study will be assigned to treatment using centralized randomization procedures stratified by time from onset of illness to study enrollment, presence of underlying chronic lung condition (asthma, COPD, history of smoking) and pre-enrollment use of symptom-relief medication. The treatment numbers will appear on the bottles containing the masked study medication. The randomization list will be masked to study participants including Sponsor, Investigators, study monitors, subjects and laboratory personnel. Unmasking for any individual subject will occur only if necessitated by emergency and knowledge of the medication being taken will influence the medical management of the subject. Furthermore, if the event warrants submission of an IND Safety Report, then the subject will be unmasked for completion of the report.

7. DATA MANAGEMENT

7.1. Electronic Data Entry

██████████ will provide the electronic data collection (EDC) system, ██████████

██████████ is a source data collection solution that will allow the site staff to record subject data on electronic protocol-driven source forms by using tablets provided by ██████████. Its purpose is to eliminate the need for data transcription into a traditional electronic case report form, and to allow both real-time access to source data by authorized Sponsor personnel and real-time edit checks.

██████████ is a mobile application for the capture of patient-reported outcomes (PROs). Study subjects will be allowed to use ██████████ on their own smartphones or a provisioned device provided by ██████████ in order to record PROs, concomitant medications and adverse events (in the form of an electronic subject diary) and to receive personalized study-specific reminders and education.

██████████ is the ██████████ web portal. It delivers real-time access to source data, and enables authorized Sponsor personnel to instantly review, clean and analyze study data.

The site staff will use ██████████ as they meet with study subjects and perform study procedures. Computerized data cleaning checks will be used in addition to manual review, including listings review, to check for discrepancies and to ensure consistency and completeness of the data. If the ██████████ system is not available for any reason, source data may be captured on paper and transcribed to the ██████████ system at a later time.

The responsible study monitor(s) will verify data, which can be performed remotely or at the clinical study site. The Investigator will ensure that the data recorded are accurate and complete.

Queries emerging during data cleaning will be generated by data management or clinical research associates in [REDACTED]. The Investigator or his/her designee will answer the queries and update the source data, if needed.

Adverse events will be coded by data management using the latest version of the Medical Dictionary for Regulatory Activities (MedDRA); medications will be coded by data management using the World Health Organization (WHO) DRUG dictionary.

After the Last Subject Last Visit (LSLV) has taken place, the database will be cleaned as necessary. As soon as the database is considered clean, it will be locked. The locked database will be used in the final statistical analysis for study reporting. Measures will be undertaken to protect subject data handled during inspections against disclosure to unauthorized third parties. Subject confidentiality will be maintained at all times.

All listings, summaries and analyses will be produced using SAS Statistical Software (SAS Institute, Inc., Cary, NC).

7.2. Protocol Deviations

Protocol deviations will be documented by the Investigator, reported to the institutional review board (IRB) as appropriate, and also reviewed by the assigned clinical research associate (CRA). Deviations will be reported in the clinical trial management system. Each deviation will be classified as major or minor according to the following definitions:

Major protocol deviation: A deviation that has an impact on subject safety, may substantially alter risks to subjects, may have an effect on the integrity of the study data, or may affect the subject's willingness to participate in the study

Minor protocol deviation: All other protocol deviations.

7.3. Data Quality Assurance

The accuracy and reliability of the study data will be assured by the selection of qualified Investigators and appropriate study centers, review of protocol procedures with the Investigator and associated personnel prior to the study, and by periodic monitoring visits by the Sponsor. Written instructions will be provided for collection, preparation, and shipment of samples.

[figure not shown]
The monitor will review the source data for accuracy and completeness, and any discrepancies will be resolved with the Investigator or designee, as appropriate.

The Sponsor will be entitled to inspect and audit the facilities used in the clinical and laboratory parts of the study, as well as to make anonymized copies of all the data files pertaining to the study. Similar procedures may also be conducted by agents of any regulatory body, either as part of a national GCP compliance program or to review the results of this study in support of a regulatory submission. The Investigator should immediately notify the Sponsor if they have been contacted by a regulatory agency concerning an upcoming inspection.

8. STATISTICAL CONSIDERATIONS

8.1. Sample Size Calculations

The Symptom Response definitions for this study will be derived from the subjects' FLU-PRO questionnaire responses as described in section 8.3 below. The FLU-PRO-derived endpoint is expected to track very closely to return to usual health status (a daily yes/no question in the FLU-PRO questionnaire), which in turn is expected to track very closely to ability to perform 100% of normal activities. We assume, therefore, that the cumulative distributions of time to Symptom Response for the placebo treatment group will closely reflect historical data from Romark Study RM08-3002 for time from first dose until the EV/RV-infected subjects report that they are able to perform 100% of usual activities (see placebo curve in chart below). Then, to calculate sample size, we assume that treatment with NTZ treatment should result in reduction of at least 48 hours in median time to symptom response. The following curves have been developed for determining sample size.

Based upon these curves, a sample size of 530 subjects with laboratory-confirmed EV/RV infection (i.e. 265 for each of the 2 groups) will provide 90% power to detect a statistically significant difference in the survival distributions between the NTZ and placebo groups (2-sided alpha of 0.05). This calculation was performed for the Gehan rank test using SAS PROC POWER (SAS 9.4) with the curves shown above (proportion not recovering by the end of each day was used as input) and censoring at day 21 (hour 504). Assuming that up to 12% of subjects will have incomplete data, we arrive at a sample size of 600 subjects in total, 300 per treatment group to yield at least approximately 530 with complete data (all 600 subjects will be included in the primary analysis with subjects with incomplete data censored as of their last entry).

Based upon these calculations, the study will enroll at least 600 subjects with laboratory-confirmed EV/RV infection up to a maximum of 700 subjects with laboratory-confirmed EV/RV infection. We estimate that this will require enrollment of up to 1,750 subjects in total assuming an EV/RV-positive rate of at least 40%.

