N (censored)	55 (1)	51 (5)	61 (5)	61 (7)
Median (IQR)	115.6 (69-210)	138.8 (83-309)	113.7 (65-179)	146.5 (92-298)
Difference vs. placebo	-30.9 (-23, -88)	-7.7 (-9, +11)	-32.8 (-27 -119)	
P value vs. placebo, Wilcoxon	0.0390	0.7015	0.0205	
P value vs. placebo, Log Rank	0.0128	0.9141	0.0660 ¹	

¹P value vs. placebo is shown for this sensitivity analysis because OST is not effective against EV/RV.

Analysis of time to alleviation of all symptoms comparing all NTZ-treated subjects (NTZ and NTZ+OST groups) to placebo-treated subjects is presented below.

Table 5: Study RM08-3002: Median (IQR) times (hrs.) to alleviation of all symptoms for subjects infected with EV/RV as sole identified pathogen, NTZ vs. placebo

Group	NTZ	Placebo
N (censored)	116 (6)	61 (7)
Median (IQR)	114.1 (65-187)	146.5 (92-298)
Difference vs. placebo	-32.4 (-27, -111)	
P value vs. placebo, Wilcoxon	0.0133	
P value vs. placebo, Log Rank	0.0161	

The magnitude of treatment benefit was larger in subjects treated earlier in the course of illness. The following table presents an analysis of time to alleviation of symptoms for subjects enrolled within 24 hours of symptom onset and for those enrolled >24 hours after symptom onset.

Table 6: Study RM08-3002: Median (IQR) times (hrs.) to alleviation of all symptoms for subjects infected with EV/RV as sole identified pathogen

Group	Enrolled ≤24 Hours from Symptom Onset		Enrolled >24 Hours after Symptom Onset	
	NTZ	Placebo	NTZ	Placebo
N (censored)	47 (4)	23 (3)	69 (2)	38 (4)
Median (IQR)	103.5 (63-212)	174.2 (114-309)	124.7 (72-181)	137.5 (79-261)
Difference vs. placebo	-70.7 (-51, -97)		-12.8 (-7, -80)	
P value vs. placebo, Wilcoxon	0.0103		0.3004	
P value vs. placebo, Log Rank	0.0493		0.1235	

Treatment with NTZ also showed benefit in analysis of time to return to ability to perform all normal activities with the median improvement being approximately 4.69 days (112.5 hours). See the table below.

Table 7: Study RM08-3002: Median (IQR) times (hrs.) to return to normal activities for subjects infected with EV/RV as sole identified pathogen, NTZ vs. placebo

Group	NTZ	Placebo
N (censored)	115 (29)	60 (22)
Median (IQR)	189.5 (109-402)	302.0 (135-643)
Difference vs. placebo	-112.5 (-26, -241)	
P value vs. placebo, Wilcoxon	0.0452	
P value vs. placebo, Log Rank	0.0326	

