4.1. Inclusion Criteria

1. Male and female subjects at least 12 years of age
2. Presence of clinical signs and/or symptoms consistent with an acute illness compatible with EV/RV infection (each of the following is required):
 - a. Presence of moderate or severe rhinorrhea defined as “attempting to relieve nasal symptoms by blowing, wiping, or sniffing at least twice per hour for any one hour within 12 hours preceding study entry,” AND
 - b. Presence of cough, sore throat or nasal obstruction.

3. Negative rapid influenza diagnostic test (required only if the subject has an oral temperature >100°F in the clinic or if the latest CDC weekly influenza report shows influenza prevalence “Regional” or higher for the institution’s state). A result from a rapid influenza diagnostic test performed on the same day that informed consent is obtained will be sufficient to meet this criterion if documentation of test results is available as part of medical history.
4. Onset of illness no more than 40 hours before enrollment in the trial. Onset of illness is defined as the first time at which the subject experienced rhinorrhea, cough, sore throat or nasal obstruction.
5. Willing and able to provide written informed consent (including assent by legal guardian if under 18 years of age) and comply with the requirements of the protocol, including completion of the subject diary

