8.4.1. Efficacy Analyses

Efficacy analyses will be based on a population consisting of all subjects that received at least one dose of study drug and had laboratory-documented EV/RV infection (infected intent-to-treat or ITTI population). Laboratory-documented EV/RV infection is defined by identification of EV/RV in nasopharyngeal secretions by RT-PCR at baseline, Day 2 or Day 3. For time to event analyses a test of significance (as described in the following) will be performed with descriptive statistics provided including the use of Kaplan-Meier figures.

There will be one primary efficacy analysis:

- Time to Symptom Response for the NTZ treatment group will be compared to that of the placebo treatment group using a stratified Gehan-Wilcoxon test ($\alpha = 0.05$) where stratification will follow that used for randomization. Subjects without a Symptom Response being recorded will be treated as censored as of their last diary without a documented Symptom Response.

If the primary analysis is significant at the 0.05 level, a key secondary efficacy analysis will be formally evaluated at the 0.05 level as follows:

- Time to Ability to Perform All Normal Activities for the two treatment groups will be compared using a stratified Gehan-Wilcoxon test ($\alpha = 0.05$) where stratification will follow that used for randomization. Subjects without an Ability to Perform All Normal Activities response being recorded will be treated as censored as of their last diary without a documented Ability to Perform All Normal Activities response.

If both the primary analysis and the key secondary efficacy analysis are significant at the 0.05 level, another secondary efficacy analysis will be formally evaluated at the 0.05 level as follows:

- Proportions of subjects experiencing one or more complications of colds due to EV/RV infection will be compared between the treatment groups using a Cochran-Mantel-Haenszel test stratified by the randomization strata ($\alpha = 0.05$).

Exploratory analyses will be performed as follows:

- For each of the 32 individual FLU-PRO symptoms, Time to Individual Symptom Response for the NTZ and placebo treatment groups will be compared using the Gehan-Wilcoxon test.
- For each of the 6 FLU-PRO domains, Time to FLU-PRO Domain Response for the NTZ and placebo treatment groups will be compared using the Gehan-Wilcoxon test.

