#### **11.2.2. Analysis of the Primary Efficacy Parameter**

The primary efficacy parameter, time to Symptom Response, will be derived as follows:

Event: Time of Symptom Response – time of the first dose

Censored: Time of last symptom assessment – time of the first dose

If Symptom Response is achieved at the time of the first symptom assessment diary record, the subject will be excluded from the analysis.

If Symptom Response is not achieved prior to a subject’s last available diary assessment, but the criteria are met at the last available diary assessment with no evidence of symptom relief medication intake during that diary period, time of Symptom Response will be considered to have occurred at the start of the last daily diary period.

Time to Symptom Response for the NTZ treatment group will be compared to that of the placebo treatment group using a Gehan-Wilcoxon test stratified by (1) time from onset of illness to time of first dose of study medication (0-24, >24-≤36, or >36 hours from onset), (2) pre-enrollment use of symptom relief medication, and (3) presence of underlying lung condition including asthma, COPD, or past or present history of smoking. The comparison will be graphically depicted using Kaplan-Meier curves.

Analysis Population(s): ITTI

Derived Variables: Event: Time of Symptom Response – time of first dose

Censored: Time of last symptom assessment – time of first dose

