### Analysis

The efficacy parameter, Time to Ability to Perform All Normal Activities, will be derived as follows:

Event: Time of Ability to Perform All Normal Activities – time of the first dose

Censored: Time of last ability assessment – time of the first dose

If Ability to Perform All Normal Activities is achieved at the time of the first ability assessment diary record, the subject will be excluded from the analysis.

If the subject does not achieve Ability to Perform All Normal Activities prior to the subject's last available diary assessment, but records a "10" for ability to perform all normal activities at the last available diary assessment with no evidence of symptom relief medication intake during that diary period, time of Ability to Perform All Normal Activities will be considered to have occurred at the time of the last available diary assessment.

Time to Ability to Perform All Normal Activities for the NTZ treatment group will be compared to that of the placebo treatment group using a Gehan-Wilcoxon test stratified

by (1) time from onset of illness to time of first dose of study medication (0-24, >24-≤36, or >36 hours from onset), (2) pre-enrollment use of symptom relief medication, and (3) presence of underlying lung condition including asthma, COPD, or past or present history of smoking. The comparison will be graphically depicted using Kaplan-Meier curves.

Analysis Population(s): ITTI

Derived Variables: Event: Time of Ability to Perform All Normal Activities – time of first dose

Censored: Time of last ability assessment – time of first dose

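### Does stratifying the primary test into 12 cells undo the 90% power stated for a Gehan test without strata?

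*Protocol*

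**What the plan says.** The sample size sections of both documents say that "a sample size of 530 subjects with laboratory-confirmed EV/RV infection (i.e. 265 for each of the 2 groups) will provide 90% power" (two-sided alpha 0.05, censoring at 504 hours). On method they say "This calculation was performed for the Gehan rank test using SAS PROC POWER", with two overall curves as input. Neither section mentions strata. Enrolment is then set at 600 to 700 infected subjects, to allow for up to 12% incomplete data.

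The analysis sections name a stratified test. In Protocol 8.4.1, time to Symptom Response on nitazoxanide "will be compared to that of the placebo treatment group using a stratified Gehan-Wilcoxon test". SAP 11.2.2 makes the comparison "using a Gehan-Wilcoxon test stratified by (1) time from onset of illness to time of first dose of study medication", pre-enrolment symptom relief medication, and underlying lung condition. SAP 11.4.1 words the key secondary analysis the same way: it "will be compared to that of the placebo treatment group using a Gehan-Wilcoxon test stratified" by those three factors. No power is stated for the key secondary endpoint, so the 90% concerns the primary endpoint only.

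The onset factor has three levels (0-24, >24-≤36 and >36 hours), and inclusion criterion 4 requires "Onset of illness no more than 40 hours before enrollment in the trial". On software, Protocol 7.1 says "All listings, summaries and analyses will be produced using SAS Statistical Software". Neither document says how the stratum statistics are combined.

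**The concern.** A reader would expect the stated power to belong to the test that will be run. For a Gehan test the difference can matter, because its weights are the numbers at risk. If raw stratum statistics are added, a large stratum counts for more than its share of subjects, and under a common effect that costs efficiency. Unequal strata are likely here: at enrolment the onset windows are 24, 12 and about 4 hours wide.

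If the loss were large, a null result could be read as evidence against the drug when the planned test had less than 90% power. The unnamed combining rule adds to the worry, since two reasonable rules can give different p-values on the same data.

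**Working it through.** **1. The plan's own figures.** The 90% cannot be reproduced, because the input curves are in a figure missing from this copy. The surrounding arithmetic holds: 530/0.88 = 602 against 600 stated (600 × 0.88 = 528), and 700/0.40 = 1,750. Using only the placebo quartiles in Protocol Table 7 (135, 302 and 643 hours) and a median gap of exactly 48 hours, four assumed curve shapes gave about 34-49% at 265 per arm. This does not test the 90%: the plan used full curves, and 48 hours is stated as a minimum. It does show how far any figure depends on the missing curves, so the comparisons below use assumed curves tuned to about 90% without strata.

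**2. Loss from raw summing under a common effect.** In stratum k, with n_k subjects, the expected Gehan statistic grows as n_k² and its variance as n_k³. Relative to the unstratified test, efficiency is

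f = (Σ n_k²)² / (N Σ n_k³), and power = Φ(√f × 3.2415 − 1.960),

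where 3.2415 = 1.960 + 1.2816 corresponds to 90%. If each statistic is first divided by stratum size, f is about 1.

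Neither document gives stratum shares. Protocol Table 6 has 70 of 177 subjects at ≤24 hours and 107 later, in a trial with a 48-hour entry window. Spreading the 107 evenly over 24 hours and cutting at 40 hours leaves 53.5 in >24-≤36 and 17.8 in >36. The shares are 49.5/37.9/12.6%.

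| Assumed shares (onset; relief medication; lung condition) | f | Power at 530 |
|---|---|---|
| All 12 cells equal | 1.00 | 90.0% |
| Table 6 cut at 40 h; 50/50; 50/50 | 0.92 | 87.5% |
| A: 40/40/20; 50/50; 35/65 | 0.89 | 86.4% |
| W: 60/30/10; 50/50; 50/50 | 0.87 | 85.5% |
| B: 60/30/10; 40/60; 35/65 | 0.78 | 81.8% |
| C: 60/35/5; 25/75; 25/75 | 0.72 | 78.8% |

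The relief-medication and lung shares have no source in the documents. B and C are stress cases.

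**3. What this formula leaves out.** It assumes the strata are not prognostic and the effect is the same in all of them. The documents point the other way on both. Protocol 1.1.1 reports longer symptom times in users of prior relief medication, and Protocol section 3 sets separate response definitions by lung condition. On early treatment, Protocol 1.2.5 says: "The magnitude of treatment benefit was larger in subjects treated earlier in the course of illness". The log ratio of medians is ln(343.7/165.1) = 0.73 at ≤24 hours against ln(278.5/214.3) = 0.26 later in Table 8 (ratio 2.8), and ln(174.2/103.5) = 0.52 against ln(137.5/124.7) = 0.10 in Table 6 (ratio 5.3). These subgroups are small.

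Simulated power in %, N = 530, 1,500 trials per row (Monte Carlo error about 0.8 points), exponential curves with a 48-hour median gap (170 vs 122 hours; 160 vs 112 in the prognostic rows). Prognostic means assumed recovery-rate multipliers of 0.8/1/1.25 by onset, 0.6 for relief medication and 0.5 for lung condition.

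| Setting | No strata | Raw sum | Scaled by size |
|---|---|---|---|
| Equal cells, common effect | 90.5 | 89.5 | 90.1 |
| Equal cells, prognostic | 90.0 | 92.7 | 92.9 |
| Table 6 onset, others 50/50, common effect | 89.8 | 86.9 | 89.5 |
| Same, prognostic | 89.9 | 89.9 | 92.4 |
| Same, effect 3 times larger at ≤24 h | 89.7 | 91.5 | 89.5 |
| Table 6 onset, others 30/70, common effect | 90.7 | 80.7 | 90.3 |
| Same, effect 3 times larger at ≤24 h | 90.3 | 87.1 | 89.4 |
| Same, prognostic and 3 times larger | 91.6 | 91.0 | 92.8 |
| Very uneven (expected cells 2 to 268), common effect | 90.8 | 75.5 | 90.1 |
| Same, 4 times larger at ≤24 h, 15% of subjects there | 89.9 | 51.7 | 88.7 |

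The raw-sum test ends up below, level with or above the unstratified test.

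**4. At the planned enrolment.** These runs use 12% early censoring and exponential curves of 302 vs 213.7 hours. That is an 88-hour gap, chosen to give 90% at 530 without strata; it is not the plan's 48 hours. Unstratified power is about 92% at 600 and 95% at 700. Raw-sum power with a common effect is 88.2% and 92.0% for A, and 81.1% and 86.6% for C. With the effect 2 to 2.8 times larger at ≤24 hours, A gives 90.5-91.1% at 600 and C gives 86.8-89.3%. Scaled statistics give 91-92% and 95% throughout.

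**The case for a change.** The best case for a change is that the text is incomplete and the repair is cheap. The 90% belongs to a test without strata, the planned test has 12 cells, and three separate sets of simulations agree that raw summing over unequal cells loses power under a common effect, by about 4 to 9 points for sets A and B. The combining rule is not named, it can move the primary p-value, and SAP section 7 wants analysis decisions settled before unblinding. A sentence and a short calculation on blinded stratum sizes would close the gap.

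The facts in this stand, but the need for a change does not follow. The direction of the difference is not established, and the settings closest to the documents' own data (Table 6 onset shares, a larger early effect, prognostic strata) mostly bring the test back to about 90% or above. The largest losses need shares that no document supports. The 51.7% case needs only 15% of subjects at ≤24 hours, against 40% in Table 6 even with a 48-hour entry window.

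The combining rule is a detail that analysts can settle before unblinding from the named test, factors and software. Both rules give a valid test at the 5% level. Scaling is steadier across settings; raw summing does better where early treatment works better and the early strata are large. The documents do not show which rule is better for this trial.

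**Conclusion.** No change follows. Sizing a trial on an overall two-curve test and analysing it with the randomization strata is a fair approximation. What is missing is a label on a planning figure. With the Table 6 onset shares and the other factors split evenly, the stratified test is within about 3 points below to 2 points above the unstratified one at 530 subjects. Set A with a common effect is about 2 points short of 90% at 600 and above 90% at 700. Stress cases lose more under raw summing and almost nothing under scaling.

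All these sizes rest on assumed exponential curves, assumed stratum shares and assumed prognostic strength. The sponsor's curves and the actual stratum sizes are not available here, so the 90% is neither confirmed nor contradicted.

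A restated figure would leave the test, endpoint, enrolment range and type I error as they are. The study was scheduled to end in April 2019 and the current SAP is dated 1 July 2019, so it could no longer guide enrolment either. Calling the 90% unstratified and naming the combining rule would be tidy reporting, but following the plan as written gives a sound primary analysis.
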